## 6.0 Inclusion and Exclusion Criteria

6.1 *Describe the criteria that define who will be **included** in your final study sample.*

*NOTE: This may be done in bullet point fashion.*

*Response: **Inclusion Criteria***

- Type 1 Diabetes for at least 1 year on stable use of continuous subcutaneous insulin infusion (CSII) or multiple (four or more) injections of insulin per day for last 3 months.
- HbA1c of 7-10% (inclusive)
- Ages 18-65 years (inclusive of ages 18 and 65)
- BMI  $\geq$  22 kg/m^2.
- Well versed in CHO counting.

6.2 *Describe the criteria that define who will be **excluded** from your final study sample.*

*NOTE: This may be done in bullet point fashion.*

*Response: **Exclusion Criteria***

- Inability to give informed consent
- Inability or refusal to comply with protocol
- Use of GLP-1 Receptor Agonists in the last 3 months or DPP-IV and SGLT-2 inhibitors therapy in the last 1 month.
- Risk for pancreatitis (e.g., history of gallstones, alcohol abuse, and hypertriglyceridemia)
- History of pancreatitis and or chronic pancreatitis
- Coronary event or procedure (myocardial infarction, unstable angina, coronary artery bypass, surgery or coronary angioplasty) or stroke in the previous 3 months.
- Congestive Heart Failure class III or IV or tachyarrhythmia.

- Hepatic disease: Severe hepatic insufficiency and/or significant abnormal liver function defined as:
  1. Aspartate aminotransferase (AST) >3x upper limit of normal (ULN) and/or alanine aminotransferase (ALT) >3x ULN
  2. Total bilirubin >2.0 mg/dL (34.2 µmol/L)
  3. Positive serologic evidence of current infectious liver disease including Hepatitis B viral antibody IGM, Hepatitis B surface antigen and Hepatitis C virus antibody
  4. Liver function tests more than 3 times the upper limit of normal
- Renal impairment (e.g., serum creatinine levels  $\geq$ 1.4 mg/dL for women, or eGFR <60 mL/min/1.73 m^2) or history of unstable or rapidly progressing renal disease or end stage renal disease.
- History of unexplained microscopic or gross hematuria, or microscopic hematuria at visit 1, confirmed by a follow-up sample at next scheduled visit.
- HIV positive
- History of gastroparesis
- History of medullary thyroid carcinoma or MEN 2 syndrome
- History of recurring UTI
- Uncontrolled thyroid disease (documented normal TSH), Cushing's syndrome, congenital adrenal hyperplasia or hyperprolactinemia.

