- Prior history of a malignant disease requiring chemotherapy or patients with a prior history of bladder cancer regardless of treatment
- Alcoholism or drug addiction.
- Hypertriglyceridemia (>400 mg/dl).
- Any other life-threatening, non-cardiac disease
- Uncontrolled hypertension (BP > 160/95 mm of Hg)
- Patients with hypotension or at risk for volume depletion due to co-existing conditions or concomitant medications, such as loop diuretics or recently donated >500ml of blood should have careful monitoring of their volume status
- Pregnant or breastfeeding patients or patient not willing to use two barrier method contraception during study period (unless sterilized or have an IUD)
- Use of hormonal medications, anti-obesity drugs or weight loss medications (prescription or OTC) and medications known to exacerbate glucose tolerance (such as isotretinoin, GnRH agonists, glucocorticoids, anabolic steroids, C-19 progestins) stopped for at least 8 weeks. Use of anti-androgens that act peripherally to reduce hirsutism such as 5-alpha reductase inhibitors (finasteride, spironolactone, flutamide) stopped for at least 4 weeks
- Presence of hypersensitivity to dapagliflozin or other SGLT2 inhibitors (e.g. anaphylaxis, angioedema, exfoliative skin conditions)
- Known hypersensitivity or contraindications to use GLP1 receptor agonists (exenatide, liraglutide)
- Known hypersensitivity to heparin/ IV catheter equipment.
- Eating disorders (anorexia, bulimia) or gastrointestinal disorders
- Having a history of bariatric surgery

- Debilitating psychiatric disorder such as psychosis or neurological condition that might confound outcome variables
- Use of an investigational agent or therapeutic regimen within 30 days of study
- Participation in any other concurrent clinical trial

6.3 Indicate specifically whether you will include any of the following special populations in your study using the checkboxes below.

**NOTE: Members of special populations may not be targeted for enrollment in your study unless you indicate this in your inclusion criteria.**

Response: NA

- Adults unable to consent
- Individuals who are not yet adults (infants, children, teenagers)
- Pregnant women
- Prisoners

6.4 Indicate whether you will include non-English speaking individuals in your study. **Provide justification if you will exclude non-English speaking individuals.**

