***Visit 2 (day 0):***

Qualifying subjects will be asked to come for the visit in a fasting state (10-12hr fasting). They will be fasting for the entire visit. 24hr urine will be collected, vitals and fingerstick blood glucose and ketones ( $\beta$ -hydroxybutyrate) using the Precision Extra glucose and ketones meter (Abbott Laboratories) and urine Ketostix (Bayer) will be measured. For MDI patients, baseline blood, spot urine, and adipose tissue will be collected. The remainder of this visits' procedures apply only to pump patients. If, ketones measure positive in blood or in urine ( $\geq 0.4$  mM in blood or  $>+1$  in urine) or fasting blood glucose  $<70$  or  $>250$  mg/dl, the acute testing will not take place and patient will be rescheduled. An IV port will be placed in order to obtain blood samples throughout the duration of the visit. Insulin infusion will be stopped, and baseline blood, spot urine, and adipose tissue will be collected. These samples will constitute the baseline for all study measurements. One of the treatment arms will be administered to the patient depending on their cohort (placebo OR exenatide  $5\mu\text{g}$  subcutaneous (same site will be used in 2nd acute study at end of study) injection OR dapagliflozin 10mg (two 5mg) oral tablets OR combination of exenatide  $5\mu\text{g}$  AND

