dapagliflozin 10mg (two 5mg) with appropriate placebos in a randomized fashion). Subjects will be fasting throughout the first 6 hr of the visit. Blood (10ml) will be collected every 30 min and spot urine every 1hr for up to 8 hours. Additional blood samples (20ml) will be collected at 1, 2, 4 and 6 and 8 hours for *MNC* isolation. A second adipose tissue biopsy will be collected at 360 min after starting the treatment. Basal insulin Infusion will be restarted at the end of the 360min sample collections, food will be provided, patient will be instructed to deliver a bolus insulin dose through bolus wizard calculator of the insulin pump after entering the grams of carbohydrates and blood glucose (Bolus wizard matches the bolus insulin dose based on individual patient's insulin to carbohydrate ratio and correction factor for high blood glucose). Patients will be monitored for at least 2hr before discharging from center (8hr time point). The subject's blood glucose and ketones ( $\beta$ -hydroxybutyrate) levels will be monitored every 30 minutes and ketones will be also measured in urine using Ketostix every hour to ensure safety. If the BG concentrations exceed 400 mg/dl or blood  $\beta$ -hydroxybutyrate exceeds 2.5mmol/l (or +3 (80mg/dl) or greater in urine) anytime during the 360 minutes following single dose/doses with or without clinical signs and symptoms of DKA like nausea and vomiting then STAT lab sample for CMP will be collected along with research blood sample. Spot urine and adipose tissue biopsy will be collected only if deemed feasible by the investigator present based on the clinical condition of the participant. Basal insulin will be restarted; bolus insulin as per the bolus wizard calculator will be administered and a meal provided. Patient will be discharged only after all laboratory parameters return to pretesting levels with no clinical symptoms of DKA.

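### The hypotension and volume-depletion entry in the Section 6.2 exclusion list asks only for monitoring, so as worded it excludes nobody (minor)

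*Combined protocol and SAP*

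**What the plan says.** Section 6.2 is headed as the list of patients who will be excluded. One entry covers patients who are hypotensive or at risk of volume depletion through other conditions or medication, and closes "such as loop diuretics or recently donated >500ml of blood should have careful monitoring of their volume status". It gives no blood-pressure figure. The entry directly above it does: "Uncontrolled hypertension (BP > 160/95 mm of Hg").

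Section 8.1 enrols patients who satisfy all criteria. Section 20.1, patient-specific item ii, allows withdrawal of a participant who develops a condition on the exclusion list.

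The full acute test in Section 10.1 (Visit 2, repeated at Visit 6) applies to pump patients only. Vitals are taken on arrival. If blood or urine ketones are positive, or fasting glucose is below 70 or above 250 mg/dl, "the acute testing will not take place and patient will be rescheduled". The stop rule begins "If the BG concentrations exceed 400 mg/dl or blood" and goes on to a beta-hydroxybutyrate limit of 2.5 mmol/l and a urine ketone limit of +3.

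Section 21.1 names volume contraction and symptomatic hypotension among the known risks of SGLT-2 inhibitors.

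**The concern.** A criterion in an exclusion list should say who stays out. This one names a group and then says how to look after them. If exclusion was intended, the closing clause defeats it. If monitoring was intended, the entry is in the wrong section, and nothing says what these patients receive beyond what everyone receives.

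What is at stake is participant safety. The protocol itself identifies these patients as vulnerable to volume loss. On the literal reading they may be fasted, taken off pump insulin, bled repeatedly and, in some arms, given a drug for which the protocol lists volume contraction as a risk. Section 22.1 states no expected individual benefit to set against this.

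The wording also carries into Section 20.1 item ii: it is unclear whether hypotension that arises during the study counts as an exclusion condition.

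**Working it through.** The plan states no figure on this point, so the check compares the texts and then sums what the acute day involves.

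**Text comparison**

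| Place | Condition | Action attached |
|---|---|---|
| 6.2, hypertension entry | BP above 160/95 | Exclusion |
| 6.2, hypotension/volume entry | No number | Monitoring only |
| 10.1 Visit 2 and 21.2, start rule | Ketones, fasting glucose | Reschedule |
| 10.1 Visit 2, stop rule | Glucose, blood and urine ketones | Laboratory sample, insulin, meal |
| 10.1 Visit 2, discharge after a stop | Laboratory values, DKA symptoms | Hold until resolved |
| 10.1 Visit 6 | Refers to Visit 2 for samples and monitoring; states no reschedule rule of its own | None added |
| 10.2 schedule, 19.2, 21.2 | BP at every visit; volume control at every visit | None stated |

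No row turns a low blood pressure or a depleted volume into exclusion, delay or stopping.

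**Fast.** Arrival after 10 to 12 h, plus the first 6 h of the visit: 10 + 6 = 16 h to 12 + 6 = 18 h.

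**Blood drawn.** The Visit 2 text gives two streams: "Blood (10ml) will be collected every 30 min and spot urine every 1hr for up to 8 hours" and "Additional blood samples (20ml) will be collected at 1, 2, 4 and 6 and 8 hours". The restart point is "Basal insulin Infusion will be restarted at the end of the 360min sample collections, food will be provided". I assume that the baseline sample is also 10 ml.

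- Up to the 360-min sample: times 0, 30, ..., 360 make 13 samples, 13 × 10 = 130 ml. The additional draws at 1, 2, 4 and 6 h are 4 × 20 = 80 ml. Sum: 130 + 80 = 210 ml, and 210/500 = 42% of the donation volume named in the 6.2 entry.
- After restart: 390, 420, 450 and 480 min, 4 × 10 = 40 ml, plus 20 ml at 8 h, giving 60 ml.
- Whole day: 210 + 60 = 270 ml, and 270/500 = 54%. The same is drawn again at week 12.

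**Sensitivity.** Without a baseline sample, the pre-restart volume is 120 + 80 = 200 ml and the day's total is 260 ml. The mononuclear-cell isolation item under Procedures in Section 10.1 gives 30 to 40 ml per sample. If that replaces the 20 ml, the pre-restart volume runs from 120 + 4 × 30 = 240 ml to 130 + 4 × 40 = 290 ml. The day's total runs from 160 + 5 × 30 = 310 ml to 170 + 5 × 40 = 370 ml. The two texts agree without any replacement if 30 ml means the routine 10 ml plus the additional 20 ml. That is an inference, so I use the Visit 2 text and give the range.

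**Exposure to dapagliflozin.** Two of the four cohort 1 arms, 2 × 15 = 30 of 60 patients, and two of the three cohort 2 groups, whose sizes are not given. The split between pump and injection users is not given either, so the number of flagged patients who reach the acute day cannot be computed.

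**The case against.** The strongest reply is that this is a drafting slip with little practical effect. The trial is single-centre, the second location only recruits and consents (Section 12.1), and the section heading makes the intent fairly plain. That stands: a reader might infer that sites will apply the entry differently, but there is only one team applying it.

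A reader might also infer that at-risk patients go unwatched. The documents do not support that. BP is scheduled at screening and at all six visits (10.2), 19.2 and 21.2 repeat the monitoring, safety data are reviewed within 1 to 2 days (21.2), and a nurse is present with an investigator available (12.1). Other entries remove some high-risk patients, such as "Congestive Heart Failure class III or IV or tachyarrhythmia" and eGFR below 60. Section 20.2 gives the investigator discretion to remove a participant. What remains is that none of this turns a low reading into a written action.

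A third tempting reading is that the lack of a blood-pressure stop rule is itself an error. The acute-day rules address the hazard that stopping insulin creates, and the lack of a further rule contradicts nothing. On-site staff would be expected to act on symptomatic hypotension. A written rule is an improvement, not a correction.

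Finally, 210 ml over 6 hours is less than half of the protocol's own 500 ml marker, and no text withholds water, so the fast should not be read as fluid restriction. Both points stand and limit the size of the concern.

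**Conclusion.** The wording defect holds: an entry in the exclusion list excludes no one as written, and patients whom the protocol flags could enrol and, if on a pump, undergo the acute day. Severity is minor. The number affected is unknown and probably small. The blood volume assumes a 10 ml baseline draw and the Visit 2 volumes.

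A reader might take this as a threat to the trial's results. Nothing in the documents supports that: sample size, alpha and the primary comparison do not depend on this entry. The point is one of eligibility wording and participant safety.

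**What to change.** **Main change.** Reword the Section 6.2 entry so that it opens with the words *At screening*, then lists hypotension, risk of volume depletion from other conditions or medication such as loop diuretics, and recent donation of more than 500 ml of blood. Delete the closing clause on monitoring.

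The screening limit is required. Without it, Section 20.1 item ii would make hypotension arising on treatment a ground for withdrawal. Those withdrawals could concentrate in the dapagliflozin arms, in a trial whose primary model uses observed data only (Section 17.1). The investigator may also set a figure for hypotension and a window for recent donation; the documents give neither, so none is proposed here.

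**Optional addition.** For Visits 2 and 6, add symptomatic hypotension or clinical volume depletion on arrival as a reason to reschedule the acute test, writing it into Visit 6 explicitly. Add the same conditions as a reason to stop the test, with their own action: stop sampling, give fluids, restart insulin and food, and discharge once blood pressure has recovered. The existing ketosis action should not be borrowed, because it includes no fluids, takes further blood and sets no blood-pressure condition for discharge.

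**Cost.** Amendment text only, since vitals are already taken at screening and on arrival. A few candidates may be lost and a few visits rescheduled.

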## 7.0 Vulnerable Populations

*If the research involves special populations that are considered vulnerable, describe the safeguards included to protect their rights and welfare.*

*NOTE: You should refer to the appropriate checklists, referenced below, to ensure you have provided adequate detail regarding safeguards and protections. You do not, however, need to provide these checklists to the IRB.*

7.1 For research that involves **pregnant women**, safeguards include:  
*NOTE CHECKLIST: Pregnant Women (HRP-412)*

Response: We will not be using subjects from vulnerable populations

N/A: This research does not involve pregnant women.

7.2 For research that involves **neonates of uncertain viability or non-viable neonates**, safeguards include:  
*NOTE CHECKLISTS: Non-Viable Neonates (HRP-413), or Neonates of Uncertain Viability (HRP-414)*

Response:

N/A: This research does not involve non-viable neonates or neonates of uncertain viability.

7.3 For research that involves **prisoners**, safeguards include:  
*NOTE CHECKLIST: Prisoners (HRP-415)*

Response:

N/A: This research does not involve prisoners.

7.4 For research that involves **persons who have not attained the legal age for consent to treatments or procedures involved in the research (“children”)**, safeguards include:  
*NOTE CHECKLIST: Children (HRP-416)*

Response:

N/A: This research does not involve persons who have not attained the legal age for consent to treatments or procedures (“children”).

7.5 For research that involves **cognitively impaired adults**, safeguards include:  
*NOTE CHECKLIST: Cognitively Impaired Adults (HRP-417)*

Response:

N/A: This research does not involve cognitively impaired adults.

7.6 Consider if other specifically targeted populations such as students, employees of a specific firm, or educationally or economically disadvantaged persons are vulnerable. **Provide information regarding their safeguards and protections, including safeguards to eliminate coercion or undue influence.**

Response: No specific populations or vulnerable groups will be targeted. All subjects enrolled in this study will be of legal adult consenting age with the ability to speak, read and understand the English language. Patients will have the ability to speak with the research team regarding any questions or concern they have before signing the consent. Patients are made aware that this study is voluntary and they are able to stop participating at any time they feel uncomfortable. Patients are not be pressured into participating and their clinic standard of care will remain the same if they participate or choose not to participate.

## 8.0 Eligibility Screening

8.1 Describe **screening procedures** for determining subjects' eligibility. Screening refers to determining if prospective participants meet inclusion and exclusion criteria.

 Include all relevant screening documents with your submission (e.g. screening protocol, script, questionnaire).

Response:

Prospective participants will be asked to read and understand the consent and any questions they may have regarding the protocol will be answered. If the subject wants to participate in the study, they will be asked to sign the informed consent form. The subject's medical history and current medications will be obtained as well as their blood pressure and vitals. A physical examination will also be done. Blood samples will be taken in order to evaluate HbA1c, CBC, CMP and liver and kidney functions and pregnancy status. The patient's insulin pump will be uploaded for pump patients, and food/insulin logs will be collected for MDI patients. Patients meeting all the inclusion and exclusion criteria based on all screening tests will be enrolled in the study.

N/A: There is no screening as part of this protocol.

## 9.0 Recruitment Methods

N/A: This is a records review only, and subjects will not be recruited. NOTE: If you select this option, please make sure that all records review procedures and inclusion/exclusion screening are adequately described in other sections.

9.1 Describe when, where, and how potential subjects will be recruited.

NOTE: Recruitment refers to how you are identifying potential participants and introducing them to the study. Include specific methods you will use (e.g. searching charts for specific ICD code numbers, Research Participant Groups, posted advertisements, etc.).

Response: Participants will be identified by prescreening clinical charts, patient doctor interaction at the time of their visits, flyers advertisements and researchmatch.org. Diabetes Endocrinology Center of WNY Locations include:

1. [name]
2. [name]
3. [name]
4. [name]

Patients will also be recruited at UBMD Pediatrics, Division of Endocrinology/Diabetes. [name]

The study clinical team will evaluate their clinic patients for possible participation in this study according to the inclusion and exclusion criteria at the Diabetes and Endocrinology Center of WNY. Patients that may qualify for the study at all sites are referred to the research team at [name] for further eligibility evaluation. Patients meeting the inclusion and exclusion criteria based on preliminary phone evaluation will be invited to participate in the study.

- Facebook and Craigslist will be used for recruitment.
- The approved study advertisement will be posted on the main advertising board at Erie County Medical Center.
- A generic flyer will also be utilized for recruiting within the Kaleida Health system.

9.2 *Describe how you will protect the privacy interests of prospective subjects during the recruitment process.*

*NOTE: Privacy refers to an individual's right to control access to him or herself.*

Response: Patient charts will be screened according to the study inclusion and exclusion criteria by our trained clinical staff and physicians. If the patient qualifies and is of consenting age, the physicians will speak to them about their interests in participating in research. If the patient agrees, their information will be given to the research coordinator to be contacted for further evaluation. All personal information will be kept confidential and locked in the coordinator office.

9.3 *Identify any materials that will be used to recruit subjects.*

*NOTE: Examples include scripts for telephone calls, in person announcements / presentations, email invitations.*

 *For advertisements, include the final copy of printed advertisements with your submission. When advertisements are taped for broadcast, attach the final audio/video tape. NOTE: You may submit the wording of the advertisement prior to taping to ensure there will be no IRB-required revisions, provided the IRB also reviews and approves the final version.*

Response: In addition to screening clinical charts, participations will be identified through; flyer advertisement, researchmatch.org, craigslist.com, and facebook.

## 10.0 Procedures Involved

10.1 Provide a description of **all research procedures or activities** being performed and when they are performed once a subject is screened and determined to be eligible. Provide as much detail as possible.

*NOTE: This should serve as a blueprint for your study and include enough detail so that another investigator could pick up your protocol and replicate the research. For studies that have multiple or complex visits or procedures, consider the addition of a schedule of events table in in your response.*

*Response:*

The study investigations include evaluation of the acute effects of a single dose of dapagliflozin (10mg), exenatide (5µg), a combination of exenatide and dapagliflozin or placebo under insulinopenic condition and the long term effect under basal conditions before and after 12 weeks treatment with dapagliflozin, Exenatide extended release, a combination of Exenatide extended release and dapagliflozin or placebo on ketogenesis, glucagon and lipolysis. This applies to the first 60 patients in cohort 1. For cohort 2, we will evaluate the acute effects of a single dose of dapagliflozin (10mg), exenatide (5µg), or a combination of exenatide and dapagliflozin under insulinopenic condition and the long term effect under basal conditions before and after 12 weeks treatment with dapagliflozin, Exenatide extended release, or a combination of Exenatide extended release and dapagliflozin on Ketogenesis.

In the acute effects study, qualified patients will come fasting to the research center. Review of study procedures and vitals will be performed. Insulin infusion (pump) will be stopped and basal blood, urine and adipose tissue biopsy samples will be obtained. Placebos, exenatide (5µg) or dapagliflozin (10mg) (with appropriate placebos) or combination of exenatide and dapagliflozin will be administered, according to a randomized fashion and cohort assigned, and blood samples will be collected every 30 min for up to 8 hours after starting the treatment. Urine will be collected every hour up to 8 hours and a second adipose tissue biopsy will be collected at 6 hours after the start of the treatment. Additional blood samples will be collected at 1, 2, 4 and 6 and 8 hour marks for MNC isolation. Plasma and mononuclear cell (MNC) fractions will be prepared from the blood samples. The patient will then come back at the 24 hour mark for a fasting blood and urine collection. The long term study will then commence. Depending on the cohort, Exenatide extended release or dapagliflozin (along with appropriate placebos) or a combination of both drugs will be started and continued for 12 weeks according to original randomization of day 0. In the long term study, dapagliflozin (or the appropriate placebo) will be started at 5mg dose and will be titrated to 10mg/day after 5 days. Fasting blood and 24hr urine samples will be collected at 1, 4 and 8 weeks. At 12 weeks, the 2nd acute effects testing study will be repeated as described above.

Drug Blinding:

All drugs used and their matching placebos will be provided by AstraZeneca in an unlabeled form. Drug or placebo assignment will be mailed separately. A designated coordinator/investigator (or University Pharmacy) who is not participating in the study will receive the drug/placebo assignment codes and will be responsible for relabeling the drugs and placebo containers/vials according to Good Manufacturing Practice and in compliance with FDA regulations and local guidelines. Relabeled drug/ placebos will be dispensed by study investigators according to pre-generated randomization log generated using Microsoft –Excel randomization feature. Records of drug and placebo assignment will be kept with the independent investigator/coordinator (or UB Pharmacy) in a secure place (locked office or enclosure) or on password protected computer and folder (if digital) For each patients and in at every dispensing visit, 2 drugs and/or placebos combo will be dispensed to maintain blinding of both patient and study team. For example, patients in the dapagliflozin only arm will receive dapagliflozin active drug tablet and exenatide (acute study) and exenatide extended release (long term) matching placebos.

Drugs will be stored in a locked cabinet or locked temperature controlled refrigerator at 4C at the research facility of the Diabetes and Endocrinology Center of WNY. IND application for use of all drugs (dapagliflozin, Exenatide extended release and exenatide) in type 1 diabetes will be submitted to FDA and no study procedure will start before all local and federal approvals are obtained.

